13.1 Source documents

Source documents shall be created and maintained by the investigation site team, as per their normal clinical routine, throughout the investigation. Source documents are the original records, including but not limited to medical records, worksheets (e.g. printouts of eCRF forms), physician or nursing notes, subject questionnaires etc. Where printouts or copies of the source documentation are used for the study, these shall be signed and dated (i.e. certified) by a member of the investigation site team.

For investigation-specific variables not normally recorded in subject's medical records, a possibility to use a combined worksheet/checklist will be made available to the investigation site. These worksheets will then, if used, constitute the source for variables not entered directly in the medical records or the eCRFs. The site will store the worksheets in the ISF. The sponsor may request a copy for remote monitoring. For variables entered directly into the eCRF, the eCRF is considered the source. To ensure consistency in the recording of source data, the use of worksheets versus entering data directly into the eCRF will be defined for each site separately depending on preferred workflow (if not directly entered into the medical record).

Additionally, a source data agreement list will be used at each investigation site to define the location of source data. This list will be completed at the first interim monitoring visit at the latest.

The principal investigator will provide direct access to source data during and after the clinical investigation for monitoring, audits, and regulatory authority review and inspections, if applicable. Permission for this direct access to source documents needs to be obtained by the investigator from the subjects, hospital administration and local regulatory authorities if required by local regulations, before starting the clinical investigation.

13.1.1 Medical records (and equivalent)

Unless restricted by national or local institutional regulations, the following information should be registered in subjects' medical records:

At study enrolment/inclusion

- Date of visit
- Study code – BC108
- Study title – *'Evaluation of clinical performance of Ponto implantation using a minimally invasive surgical technique – a prospective multicentre study'*
- Subject ID (i.e. the numerical code given at enrolment/inclusion)
- Date of enrolment/inclusion (if different from visit date)
- Information that subject has signed informed consent
- Diagnoses of relevance for the investigation – past and current

At follow-up visits (incl. final visit):

- Date of visit(s)
- Study code – BC108
- Visit interval (screening, surgery, 9 days, 5 weeks 3, 6, or 12 months), including a statement of study termination, if applicable
- Results of study-related assessments required to be documented in the medical records according to the 'Source data agreement list'.

oticon MEDICAL	Title BC108 CIP MONO	Document no Doc-00068506	Revision 2	Page 38(48)
--------------------------	--------------------------------	------------------------------------	----------------------	-----------------------

- Information on adverse events (AE) – diagnosis (or signs/symptoms), start and stop dates, assessments on whether event is serious and/or related to the surgical procedure or the devices included in the investigation, and the outcome of the event.

13.2 Case Report Form recording and Processing

Data captured will be recorded, by the investigator and/or delegated site staff, in eCRFs by means of an EDC-system (SMART-TRIAL), provided/hosted by an external party (MEDEI ApS, Copenhagen, Denmark). The system has built-in features that enables users to be GCP and GDPR compliant. All data in relation to SMART-TRIAL is stored on secured Microsoft Azure hardware located in the EU, i.e. Dublin, Ireland. All users of the EDC system have personal accounts, accessed by two-factor authentication, allowing tracking of all data entries and changes in the system (i.e. audit trail).

All data, subject- and product-related, must be accurately recorded in a timely manner (i.e. within 5 working days) into the EDC system by the delegated site staff.

NB. For Serious Adverse Events (SAE), Serious Adverse Device Effects (SADE) stricter timelines applies, see section 19.3.1 for further reference.

All entered data must be consistent with the source documents, and if any discrepancies are found they must be corrected or explained in writing where applicable.

The patient reported outcome (PRO) instrument used in this investigation will be completed on paper forms by the subjects themselves. The forms (i.e. source documents), marked with the Subject ID, will then be transferred by manual data entry to the corresponding form in the EDC-system by an authorized member of the investigation site team.

13.3 Data management

Data management-related activities, e.g. data cleaning and query handling, will be performed remotely on a regular basis within the EDC-system during the investigation. Once all data for the primary endpoint (three months) or at the end of study (12 months) has been captured and recorded by the investigation site team, verified and validated by the appointed sponsor representatives, the database will be locked before any data analysis.

13.4 Storage of data

Readable copies of the site's eCRF data, either in printed form or in a digital format, as per the site's preference, will be archived in the ISF at the study site after study closure. Oticon Medical will not at any time point be in control of the eCRF data archived in the ISF, unless only for the purpose of delivering it to the study site.

The investigator should retain clinical investigation records (including medical records) according to regulatory requirements or for at least 10 years after completion or premature termination. The principal investigator must take measures to prevent accidental or premature destruction of these documents and at the end of the storage period, acquire a confirmation from the sponsor before proceeding with the destruction of the documentation.

The complete study database, which is a part of the TMF, will be securely stored at Oticon Medical, with restricted access. The TMF will be retained for 10 years after the last device covered by the investigational product's CE-mark has been placed on the market, or in accordance to national regulations, whichever is most stringent.

14 AMENDMENTS TO THE CIP

If changes to the CIP are needed, proposed amendments to the CIP shall be agreed upon between the sponsor and principal investigator, and/or the coordinating investigator. Substantial amendments should be approved by the Ethics Committee (EC) before incorporated. In addition, substantial amendments to the Patient Information and Consent Form and/or other applicable documents previously approved by the EC must be approved by the EC before they will come into effect. For non-substantial amendments, local regulations regarding notifications to EC should be followed.

15 DEVIATIONS FROM CLINICAL INVESTIGATION PLAN

A CIP deviation is an intentional or unintentional failure to follow the requirements of the CIP. Every effort should be made to comply with the requirements of the CIP and the Investigator, and other representatives of the investigational site team, is not allowed to deviate from the CIP, unless needed to protect the rights, safety and well-being of the subjects (i.e. emergencies). Under these circumstances, deviations from the CIP may proceed without prior approval by the Sponsor and favourable opinion from EC. Such cases should be documented and reported to the EC, as per local requirements, and to the Sponsor as soon as possible, but in no event later than 5 working days after the emergency occurred.

If other deviations occur, the Investigator should inform the monitor/clinical trial manager and make a record in the CIP Deviation Log provided in the ISF. The implications of the deviation must be reviewed and discussed between the Sponsor and the Investigator. If deviations are found during monitoring visits, they should also be documented in the monitoring report and handled as above. This should be done as soon as possible after detection to avoid repetitive deviations. Continuous review of protocol deviations during monitoring visits aim to detect systematic errors and to identify retraining needs at the site. Frequency of monitoring is described in the monitoring plan and should be increased if systematic deviations are identified. All protocol deviations must be documented stating the reason, date, the action(s) taken, and the impact for the subjects and/or the study. If serious or repeated deviations occur, the Sponsor has the right to initiate early termination of the study at the site(s) concerned.

At the end of the study, or in connection to a predefined interim analysis, protocol deviations will be categorized as minor or major and their consequence on analysis populations will be determined.

16 DEVICE ACCOUNTABILITY

The MONO Surgery kit will be delivered to the hospital as per hospital routine, or by a sponsor representative, and kept in a locked area. The sponsor will keep records of the delivered investigational devices. A device accountability log will be held on site including date of reception and date on return (if applicable).

All unused investigational devices must be returned to the sponsor when treatment of the last subject has been completed. Return of devices at the end of the investigation will be logged by sponsor in sponsor records.

The monitor will verify the accountability process at the monitoring visits.

17 STATEMENTS OF COMPLIANCE

The clinical investigation will be performed in consistency with the current version of the Declaration of Helsinki, ISO 14155, the Medical Device Directive (MDD) 93/42/EEC, Regulation (EU) 2017/745 (MDR) and applicable regional or national competent authority requirements as well as any additional requirements imposed by the EC.

The clinical investigation plan, including the final version of the Patient Information and Consent Form, must be approved in writing by an EC before enrolment of any subject into the investigation. The Principal Investigator is responsible for informing the EC of any amendment to the investigation plan as per local requirements.

The clinical investigation will not be commenced until approvals from the applicable EC have been received.

Any additional requirements imposed by the EC or national regulations shall be followed.

17.1 Insurance

The sponsor will be responsible for ensuring adequate insurance covering any injuries to the subject caused by the investigational device.

Oticon Medical has a Public and Product Liability Insurance (Policy number: DKLSCA03184), issued by CHUBB, that includes coverage of clinical trials.

17.2 Financing of the clinical investigation

Separate financial agreements with each study site's institution have been agreed. In brief, the study is fully sponsored by Oticon Medical AB. The investigational device is provided for free and compensation is based on the patient visit schedule at the clinics.

18 INFORMED CONSENT PROCESS

The principal investigator will ensure that the potential subject is given full and adequate oral and written information about the nature and purpose of the investigation, including possible risks and benefits involved. Alternatives to the treatment suggested in the CIP must be discussed to allow the potential subject to have an informed choice. Potential subjects must also be notified that they are free to decline participation in the investigation, and that they are free to discontinue at any time, without any consequences to their future care. Sufficient time will be given for consideration and the opportunity to ask questions before signing the informed consent form will be provided. The signed informed consent must be obtained before conducting any procedures specific for the investigation.

By signing the informed consent form, the subject agrees to participate in the investigation and that the results obtained may be used in authority assessments, and/or submissions for presentation or publication in scientific meetings and/or journals, with the condition that privacy and confidentiality are preserved. The subject also agrees that concerned personnel, the sponsor, external monitor (if assigned), and concerned authorities may have access to the patient's medical record to perform source data verification and other quality control measures, if applicable.

In the patient information sheet, information will be given on which legal bases, as given in Regulation (EU) 2016/649 (GDPR) [19], articles 6 and 9, that allows Oticon Medical to collect, process and archive subjects' personal data (including special categories of data, i.e. sensitive data).

Alternatively for UK citizens, the Data Protection Act 2018, which is the UK's implementation of the EU General Data Protection Regulation (GDPR), will be adhered to.

The signed original of the consent form must be filed in the ISF. A copy of the Patient information sheet including the signed informed consent form should be given to the patient.

If any new information becomes available during the investigation that possibly could influence the subjects' willingness to participate, they will be informed and asked to sign a revised informed consent, if applicable.

19 ADVERSE EVENTS, ADVERSE DEVICE EFFECTS AND DEVICE DEFICIENCIES

19.1 Adverse Event

An adverse event (AE) is defined as any untoward medical occurrence, unintended disease or injury or any untoward clinical signs (including an abnormal laboratory finding) in subjects, users or other persons, in the context of a clinical investigation, whether or not related to the investigational medical device.

Note 1. This definition includes events related to the investigational medical device or the comparator.

Note 2. This definition includes events related to the procedures involved.

Note 3. For users or other persons, this definition is restricted to events related to the use of investigational medical devices.

19.1.1 Serious Adverse Event

A serious adverse event (SAE) is an AE that led to any of the following:

- a) death,
- b) serious deterioration in the health of the subject, users or other persons as defined by one or more of the following:
 - 1. a life-threatening illness or injury, or
 - 2. a permanent impairment of a body structure or a body function including chronic diseases, or
 - 3. in-patient or prolonged hospitalisation, or
 - 4. medical or surgical intervention to prevent life-threatening illness or injury or permanent impairment to a body structure or a body function
- c) foetal distress, foetal death or a congenital abnormality or birth defect including physical or mental impairment

Note: Planned hospitalisation for a pre-existing condition, or a procedure required by the CIP, without serious deterioration in health, is not considered a serious adverse event.

19.1.2 Adverse Device Effect

An adverse device effect (ADE) is an adverse event related to the use of an investigational medical device.

Note 1: This definition includes adverse events resulting from insufficient or inadequate instructions for use, deployment, implantation, installation, or operation, or any malfunction of the investigational medical device.

Note 2: This definition includes any event resulting from use error or from intentional misuse of the investigational medical device.

19.1.3 Serious Adverse Device Effect

A serious adverse device effect (SADE) is an ADE that has resulted in any of the consequences characteristic of a serious adverse event (see section 19.1.1).

19.1.3.1 Unanticipated Serious Adverse Device Effect

An unanticipated serious adverse device effect (USADE) is a SADE which by its nature, incidence, severity or outcome has not been identified in the current version of the risk analysis report.

Note: Anticipated Serious Adverse Device Effect (ASADE) is an effect which by its nature, incidence, severity or outcome has been identified in the risk analysis.

19.2 Device deficiency

A device deficiency (DD) is defined as any inadequacy of an investigational medical device related to its identity, quality, durability, reliability, usability, safety or performance.

Note 1: Device deficiencies include malfunctions, use errors, and inadequacy in the information supplied by the manufacturer including labelling.

Note 2: This definition includes device deficiencies related to the investigational medical device or the comparator.

Note: To distinguish between a DD and an ADE it may be useful to consider DDs as not directly affecting or involving the subject.

19.3 Reporting of Adverse Event(s)

All health problems*, whether judged as related to the surgery and/or the Ponto products or not, that are reported by the subject, found in medical records or found at the clinic visits must be recorded by the PI, or authorised designee, in the eCRF as an AE, preferably within 5 working days. For events judged as related, i.e. ADEs, additional information is required as specified in eCRF.

**except those defined and excluded from the investigation.*

19.3.1 *Reporting of Serious Adverse Event / (Unanticipated) Serious Adverse Device Effect*

In addition to the information already collected and recorded for AEs/ADEs, there are more detailed information required for SAEs/SADEs/USADEs as specified in eCRF.

For SAEs/SADEs/USADEs the Investigator must:

- Record SAE/SADE/USADEs details in the eCRF immediately, but no later than **24 hours** after becoming aware of the event. An email to Oticon Medical will automatically be generated by the EDC system after investigator signing of the SAE form by the Investigator. In addition, an email shall be sent to responsible clinical trial manager (to notify the SAE/SADE/USADE).
- Follow up the initial SAE/SADE/USADEs information as soon as new information is available.
- Report SAE/SADE/USADEs to the EC according to local requirements (e.g. per event and/or annually). In multicentre investigations this may include the SAE/SADE/USADEs reported from another site; this information will be provided by Oticon Medical, if required.
- Provide Oticon Medical with all SAE/SADE/USADEs related documentation and correspondence to the EC.

19.3.1.1 Reporting of Unanticipated Serious Adverse Device Effect

The occurrence of USADEs could suggest that the clinical investigation places subjects at increased risk of harm than was to be expected beforehand. It is a sponsor obligation to handle and report USADEs to applicable authorities.

19.3.2 Device deficiency reporting

The Investigator is responsible for recording the following in the CRF/eCRF, preferably within 5 working days, for all device deficiencies:

- Device deficiency details (e. g. date and description of occurrence)
- Device deficiencies that might have led to a SADE if:
 - suitable action had not been taken or
 - intervention had not been made or
 - if circumstances had been less fortunate

For device deficiencies that might have led to a SADE, the Investigator must provide Oticon Medical with detailed information in the DD-section of the eCRF and perform the applicable steps described for SAE/SADE reporting (section 19.3.1).

19.4 Non-reportable events

When performing a BAHS surgery, some intra- and post-operative events are more or less likely to occur (i.e. not 'untoward' per se) (see sections 10.2.3 and 10.3.5). Therefore, in this investigation, the following events will be captured in the eCRF on the applicable study visit. To avoid double-reporting, these events will not be recorded in the AE log, unless the investigator judges them to exceed the level of what is to be expected (i.e. 'untoward' per se):

During surgery;

- Drilling into veins
- Drilling into air pockets
- Dura mater exposed

Post-operative complications

- Bleeding or hematoma
- Pain or numbness
- Skin dehiscence
- Erythema
- Edema
- Granulation tissue
- Skin reactions
- Revision surgery

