6.2 Justification of the investigation design and outcome measures

The investigation has a single-arm design, reflecting the typical study design in the field. The investigational device is used within its intended purpose and for patients within its indicated use. The investigation sites are renowned clinics with ENT specialists experienced in BAHS implantations and follow-up, ensuring professional patient recruitment and care. The visiting schedule follow the standard practice at the respective clinics and includes 1-3 extra visits compared to patients treated outside of the investigation, enabling close follow-up on performance and safety.

The primary endpoint of the investigation is the capability of the implant/abutment complex to provide a reliable anchorage for the sound processor three months after the MONO surgical procedure. It is comprised of five variables related to the performance and functionality of the implant/abutment complex. All variables included in this composite endpoint are commonly assessed in clinical investigations, underscoring its scientific relevance.

The safety objective is to investigate the occurrence and seriousness of adverse events (AE) related to the investigational device and corresponding procedures. The safety endpoint comprises adverse events, occurring both intra- and post-operatively.

The primary endpoint is set at three months, which is considered as a relevant time period for evaluation of the outcomes after a surgical procedure. Once osseointegration of the implant has been achieved, and the primary healing of the surgical wound has occurred, the surgical technique used is not deemed to influence the capability of the implant to provide a reliable anchorage for the sound processor. It is therefore sufficient to evaluate only short-term data. Data will also be compiled after a 12-months period, to confirm longer-term safety and performance of the devices.

The results of the investigation will be important for the understanding of outcomes related to the BAHS treatment in general and for the MONO surgical procedure and the subsequent performance of the implant/abutment complex in particular.

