8.3 Safety objective

Safety objective	Corresponding primary endpoint/outcome variable(s)	Section
L. To investigate the occurrence and severity of adverse events related to the investigational device and associated procedures	1. Number and severity of related adverse events reported from surgery throughout the investigation at 3- and 12 months	10.4
	2. Number and severity of device deficiencies reported from surgery throughout the investigation at 3- and 12 months	10.4

CONFIDENTIAL

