10.2.3 Intra-operative events

During the surgery intra-operative events and complications will be assessed by the surgeon.

Expected intra-operative events and complications includes, but are not limited to:

- Skin and bone bleedings
- Vein and sigmoid sinus exposure or damage
- Dura exposure or damage
- CSF leakage
- Insufficient bone volume or unexpected anatomy
- Angled insertion of the implant
- Re-positioning of the implant from initially chosen location (drilling at more than one site)
- Adding/using extra material at the implant site, like bone wax or Gore-tex.

Note: If an event is judged as untoward (exceeding what is normally expected according to surgeon's judgement) it should be reported as an adverse event.

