10.4 Safety assessment

Subjects will be observed and asked about 'any health problems since last visit' during all visits in the investigation. Information that will be collected includes:

- Event description
- Start and stop dates
- Action taken due to the event
- Clinical outcome of event
- Serious: no/yes (if 'yes' more information is required)
- Device/procedure related: no/yes (if 'yes' more information is required)

All occurring adverse events will be registered, tabulated and accounted for in a safety data listing. The safety endpoint will consist of a descriptive summary, including frequency, causality, severity and duration of related events at three and 12 months after surgery. See section 19 for further reference.

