12.3 Statistical methods and analytical procedures

Descriptive statistics will be used. The primary endpoint will be presented both as number and percentage, and by point estimates of the proportions combined with a two-sided 95% CI.

For secondary endpoints, the distribution of categorical and dichotomous variables will be presented both as number and percentage, although the composite variable will be presented as for the primary endpoint. Data will be presented for each time separately as well as across visits, where applicable. The distribution of continuous variables will be given as Mean, standard deviation (SD), Median, Minimum and Maximum.

For the safety endpoint, device deficiencies, adverse events and serious adverse events related to the device will be descriptively reported using frequency tables and listings.

All statistical analyses are to be explained in detail in a statistical analysis plan (SAP). Any deviations from the original analysis plan will be described in a CIP amendment, as deemed appropriate.

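### Do intra-operative events such as dura exposure drop out of the safety results because they are kept out of the adverse event log?

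*Combined protocol and SAP*

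**What the plan says.** Section 19.4 names 11 events that are captured on the eCRF form for the visit concerned, and states that "these events will not be recorded in the AE log, unless the investigator judges them to exceed the level" of what is to be expected. Three are intra-operative and eight post-operative, revision surgery among the latter. The reason given is to avoid reporting the same event twice.

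Section 10.2.3 has the surgeon assess intra-operative events, with eight non-exhaustive examples. Its closing note begins "If an event is judged as untoward (exceeding what is normally expected according to" the surgeon's judgement; such an event then becomes an adverse event.

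On the safety endpoint, section 6.2 says "The safety endpoint comprises adverse events, occurring both intra- and post-operatively". Objective L in section 8.3 is "To investigate the occurrence and severity of adverse events related to the investigational device and associated procedures". Its first endpoint is "Number and severity of related adverse events reported from surgery throughout the investigation at 3- and 12 months" and its second covers device deficiencies.

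On output, section 12.3 says that "adverse events and serious adverse events related to the device will be descriptively reported using frequency tables and listings", and leaves detail to a separate SAP. Section 10.4 says "All occurring adverse events will be registered, tabulated and accounted for in a safety data listing", and collects one relatedness item that covers device and procedure together. The statistical methods entry in the synopsis gives categorical and dichotomous variables as number and percentage, with no restriction to endpoints.

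**The concern.** The investigational device is a one-step drill kit, so what happens during drilling is the outcome closest to it. Section 7.1.2 says that no clinical data exist on the final design and that the probability of harm may differ from that of existing systems. The drill depth is 4.75 mm and inclusion requires an expected bone thickness above 5 mm, so the nominal margin can be little more than 5 − 4.75 = 0.25 mm. A reader will want to know how often the dura was exposed or a vein entered.

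Read strictly, sections 8 and 12.3 do not promise that number. An intra-operative event reaches the safety endpoint only if the surgeon calls it untoward and it is then judged related, and that judgement may differ between seven sites. The post-operative items in section 19.4 mostly have their own secondary endpoints, but the intra-operative ones have none. The report could therefore follow the plan to the letter and omit them.

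Two smaller points appear alongside. Revision surgery has no named endpoint when the implant is kept. Section 12.3 speaks of events related to the device, while objective L adds the associated procedures.

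**Working it through.** The plan gives no rate for any of these events, so there is no figure of its own to reproduce. The check traces each event from collection to output.

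**1. Endpoint rows in section 8.** Primary: A.1, which is 1. Secondary: B.1, C.1, D.1, E.1 to E.7, F.1, G.1, H.1, I.1, J.1 and K.1, which is 3 + 7 + 6 = 16. Safety: L.1 and L.2, which is 2. Total 1 + 16 + 2 = 19. Rows naming an intra-operative event: 0. Objective F covers post-operative visits only, and objective I is length of surgery.

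**2. Items in section 19.4.** 3 intra-operative + 8 post-operative = 11.

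| Post-operative item | Reported under |
|---|---|
| Bleeding or haematoma | F (10.3.5) |
| Pain or numbness | G, H |
| Dehiscence | E.6 |
| Erythema | E.1, E.4 |
| Oedema | E.4 |
| Granulation | E.1, E.4 |
| Skin reactions | E.1 to E.3 |
| Revision surgery | no named row; see step 5 |

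So 7 of 8 have a named home. The 3 intra-operative items have none in section 8.

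**3. Are the data there?** Yes. Sections 10.2.3 and 19.4 place them in the eCRF, and Table 4 schedules intra-operative events at visit 2, together with adverse event assessment.

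**4. Does any text lead to an output?**
- Intra-operative events are categorical variables, so the synopsis rule gives them number and percentage.
- The reason in section 19.4 makes sense only if the visit forms are themselves reported.
- Absence from section 12.3 shows little. The baseline characteristics in 10.1 and several surgical variables in 10.2 (bone quality, insertion torque, punch size, anaesthesia) have no endpoint row or named output either, and nobody would expect them to go untabulated.

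**5. Revision surgery.** Three routes exist. Objective F covers post-operative events in general. Loss of the implant counts as a failure under 12.4. Section 10.3.4.3 plans to compare the treatment given with the IPS advice, which includes revision. Only a revision with the implant kept and for a reason outside the IPS advice depends on objective F alone.

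**6. Relatedness.** Section 12.3 says device; 8.3 says device and procedures; 10.4 tabulates every adverse event. Section 19.3 equates events judged related, surgery included, with adverse device effects, and 19.1.2 extends that term to implantation, installation and use error. The phrase in 12.3 may also qualify only the serious events. On any reading, the listing in 10.4 contains the procedure-related events.

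**7. What a count would add (illustration; the counts are assumed).** Exact 95% limits for x events in n = 50 operated subjects are Beta⁻¹(0.025; x, n − x + 1) and Beta⁻¹(0.975; x + 1, n − x).
- x = 0: lower limit 0; upper limit 1 − 0.025^(1/50) = 7.1%.
- x = 5: estimate 10.0%, limits 3.3% and 21.8%.

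If no event were judged untoward, the adverse event table would look the same in both cases. The table of the surgery form would tell them apart.

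**The case for a change.** The strongest case for a change is that the omission is exact and the remedy cheap: one descriptive table from data already held, for the outcomes nearest to the device, where the alternative is an individual judgement across seven sites. The double-reporting argument also fails on its face for the intra-operative items, since sections 8 and 12.3 name no second place where they are reported. The synopsis rule is general, and section 12.3, which is the more detailed text, attaches its version to the secondary endpoints.

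What stands is the literal point: no endpoint row and no line in 12.3 names these events. The value of a stated count, as in step 7, also stands.

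What does not stand is that the count would otherwise be lost. Nothing in the plan excludes these data from reporting; section 19.4 only settles which form they are entered on. The filter itself follows the protocol's definition of an adverse event as an untoward occurrence (19.1), and the concern does not ask for that filter to change. The safety context is also less one-sided than it first appears: section 7.1.2 anticipates no new risks, and section 4.2 gives a shallower drill depth than the 4.9 mm of the existing minimally invasive technique.

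**Conclusion.** No change to the plan follows. The gap is one of written detail, which the analysts would fill when they tabulate the surgery form. In size it is 3 of 11 items in section 19.4, and the 8 examples in 10.2.3, without a named row among 19. The number of events affected cannot be computed, because the plan gives no rates. No estimate, confidence interval, sample size or item of data collection depends on it.

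The revision-surgery point is largely met by objective F, by the failure rule in 12.4 and by the IPS treatment comparison. The wording on relatedness in section 12.3 is a clerical mismatch with 8.3 and 10.4 that removes no event from the listings.

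This rests on two assumptions: that the general rule in the synopsis is applied to the surgery-visit variables, and that the separate SAP, which is not in the document reviewed, does not exclude them. If the SAP did exclude them, the point would have to be reopened.
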